5.7.2.2 Primary Analysis

The two primary endpoints will be tabulated with two-sided 95% CIs separately using the Clopper Pearson exact method for the FAS.

Castrate levels of serum testosterone will be summarized with descriptive statistics. Value below the lower limit of quantification (LLOQ) will be substituted by the LLOQ value for summary. Whether castrate level of serum testosterone is achieved (Yes/No) will also be summarized by visit.

Individual testosterone level data versus visit will be plotted by participant on a semi-logarithmic scale on the FAS with a dash line to indicate the testosterone limit of castration (50 ng/dL or 1.735 nmol/L) and a second dash line for the LLOQ. The arithmetic mean (\pm SD) and median testosterone levels versus visit will also be presented.

A testosterone level will be listed on all participants enrolled by participant and visit. All values below the limit of quantification will be listed as such.

5.7.2.3 Sensitivity Analysis

In addition, to further validate the analysis results of the primary endpoint, below sensitivity analyses will be conducted.

Sensitivity analysis 1: Analysis defined in section [5.7.2.2](#) (primary analyses for co-primary endpoints) will be repeated on the PPS.

Sensitivity analysis 2: Survival analysis to estimate the percentage of participants maintaining castrate levels from Week 8 to Week 24

Percentage of participants with castration levels (<50 ng/dL or 1.735 nmol/L) from Week 8 to Week 24, treated as a time-to-event endpoint, will be analysed by Kaplan-Meier method.

The event is defined as occurring in participants with a testosterone level \geq 50 ng/dL or 1.735 nmol/L between Week 8 and Week 24 (escape event), and it will be presented as number of participants with escape event (event number), percentage of participants with escape event, achievement (<50 ng/dL or 1.735 nmol/L) rate by Week 8, Week 12, Week 16, Week 20, and Week 24 along with 95% CIs (calculated using the Greenwood's formula), minimum, maximum, median and 95% CI for median (calculated using Brookmeyer-Crowley method).

To accommodate drop-out and missing values the following censoring rules will be observed:

Table 5.1 Data Censoring Rules

Subject Discontinued	Week 8 - Week 24/Day of Discontinuation		To Be Handled As
	≥ 1 Missing Testosterone Value	Any Escape*	
Yes	No	No	Censored on day of last measurement
Yes	No	Yes	Event on day of first escape
Yes	Yes	No	Censored on day of last measurement before the first missing
Yes	Yes	Yes	Event on day of first escape
No	No	No	Censored on day of last measurement (date of EOS or Day 169)
No	No	Yes	Event on day of first escape
No	Yes	No	Censored on day of last measurement before the first missing
No	Yes	Yes	Event on day of first escape
No achievement by Week 8			Event on day of Week 8

*The escape (event) is defined as participant with castrate levels of serum testosterone ≥ 50 ng/dL or 1.735 nmol/L.

Below 3 percentages based on different populations are considered for calculation of percentage of participants maintaining castrate levels from Week 8 to Week 24:

Sensitivity analysis 3: All participants treated who complete the study or premature discontinuation from the intervention period due to any reasons will be included.

Sensitivity analysis 4: Participants in the FAS or PPS who do not discontinue from the treatment period prematurely due to drug-related reasons will be included.

Sensitivity analysis 5: Participants in the FAS or PPS without any missing data from Week 8 to Week 24 will be included.

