2.3 Sample Size Determination and Power

The sample size was estimated based on data from the previous Study DEB-TRI6M-301, 97.5% of participants achieving castration and 93% of participants maintaining castration from Week 8 to Week 24.

Sample size is calculated to fulfil the co-primary efficacy criteria of this study, which is to assess the proportion of participants achieving castrate levels of testosterone on Day 29 and the proportion of participants maintaining the castrate levels of serum testosterone from Week 8 to end of Week 24. A total of 195 participants with advanced prostate cancer will be enrolled to receive the triptorelin pamoate 22.5 mg 6-month formulation.

For an exact binomial test of a proportion with a two-sided nominal significance level of 0.05 and null proportion of 85%, a sample size of 165 participants has an exact power of 88.3% when the true proportion is 93% (of participants maintaining castration from Week 8 to Week 24). This sample size of 165 participants has a power >99.9% when the true proportion is 97.5% (of participants achieving castrate testosterone levels). Exact two-sided 95% confidence interval (CI) for a binomial proportion was computed by Statistical Analysis System (SAS) using the exact binomial distributions.

Assuming the dropout rate will be around 15%, a sample size of 195 participants in total is planned for this study.

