4 ANALYSIS SETS

Screened Set

The screened set will contain all participants screened (i.e. who signed the informed consent).

Full Analysis Set (FAS)

The FAS will contain all treated participants who complete the study or is a treatment failure. Completing the study is defined as having serum testosterone measurement at baseline, Day 29 and Day 169. Treatment failure is defined as escaping castration (testosterone level ≥ 50 ng/dL or 1.735 nmol/L) at any assessments on and after Day 29 during the study, or premature discontinuation from the intervention period due to drug-related reasons (adverse event or death).

Per Protocol Set (PPS)

The PPS will contain all participants in the FAS who have no impacting major protocol deviations (i.e. that could potentially affect the primary efficacy endpoint outcome for the participant) as described in the protocol deviations document.

Safety Set

The safety set will contain all participants who receive the single dose of study intervention.

Rich PK Analysis Set (for non-compartmental analysis)

The rich PK analysis set will contain all participants in the PK/PD subset who receive one dose of study intervention, have no major protocol deviations affecting the PK variables, and who have a sufficient number of plasma concentrations to estimate the main PK parameters (maximum observed plasma drug concentration (C_{max}), time to maximum observed drug concentration (t_{max}) and area under the plasma concentration time curve (AUC)).

The criteria of major protocol deviations affecting the PK variables will be defined in the protocol deviation document. The process to review major protocol deviations potential impact on PK parameters will be ongoing and the final Rich PK Analysis Set will be determined during data review meeting.

Population PK Analysis Set

The population PK analysis set will contain all participants who received one dose of triptorelin and who have at least one triptorelin plasma concentration and no major protocol deviations affecting PK variables.

Rich PD Analysis Set

The rich PD analysis set will contain all participants in the PK/PD subset who have a sufficient number of PD (testosterone) measurements to estimate the main PD parameters (maximum observed concentration (C_{max}), time to maximum observed concentration (t_{max}) and time to castration (t_{castr})).

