- (a) In participants escaping castration at a certain visit (The escape event is defined as participant with a testosterone level >50 ng/dL), subsequent missing data is irrelevant; that is to say, participant will be treated as failure in that case.
- (b) Participants maintaining castration up to a certain visit with missing data afterwards (drop-out due to non-drug-related reasons) will be excluded from the analysis.
- (c) Participants maintaining castration up to a certain visit with missing data afterwards (drop-out due to drug-related reason) will be treated as having escaped castration (failure). Drug-related reason for drop-out is drug-related adverse event or death.
- (d) Missing data at 1 or more visit(s) between two visits where castration levels are maintained will be handled as missing for that particular visit, and the participant will be considered to have maintained castration if all visits with available results are maintained.

To derive the percentage of participants maintaining castrate levels of testosterone, assessable participants are defined as the number of participants having values at all visits and all participants having missing data according to the criteria a), c) and d) mentioned above. Participants having missing data according to the criteria b) will be excluded from this calculation. Participants who discontinue before Week 8 will also be excluded from this calculation.

Because this is a descriptive post-approval commitment study, and the protocol was approved before National Medical Products Administration (NMPA) implementation of ICH E9 (R1), estimands will not be considered for this study.

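### The Kaplan-Meier sensitivity analysis of maintenance censors castrate men who leave from Week 8 on for a drug-related reason, although the FAS definition and primary rule (c) count them as failures

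*SAP*

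**What the plan says.** Three parts of the SAP bear on a man who is castrate and leaves for a drug-related reason.

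- **FAS (SAP section 4; same in protocol 9.3).** The set holds completers (testosterone at baseline, Day 29 and Day 169) and treatment failures. Failure means escape on or after Day 29, or "premature discontinuation from the intervention period due to drug-related reasons (adverse event or death").
- **Primary maintenance rule (c) (SAP 5.7.2.1; protocol 9.4.2).** "Participants maintaining castration up to a certain visit with missing data afterwards (drop-out due to drug-related reason) will be treated as having escaped castration (failure"). Men who leave for other reasons while castrate are excluded under rule (b). Under rule (d), a gap between castrate visits still counts as maintained. The SAP adds that men who discontinue before Week 8 are left out of this calculation.
- **Sensitivity analysis 2 (SAP 5.7.2.3).** It is titled as an estimate of the same maintenance percentage. "The event is defined as occurring in participants with a testosterone level" of at least 50 ng/dL between Week 8 and Week 24. Table 5.1 sorts men by discontinued, any missing value and any escape, each yes or no. A man who discontinued without escape is censored at his last measurement or, if a value is missing, "Censored on day of last measurement before the first missing". The only other event is non-achievement by Week 8.

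The analysis names no population, so the default in SAP 5.7.1 applies: FAS and PPS.

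**The concern.** The plan defines two kinds of failure, and this analysis turns one of them into censoring while keeping the co-primary's name. Kaplan-Meier censoring assumes that a man who leaves would have gone on to escape at the same rate as those who stayed. That is hard to defend for a man removed by a drug-related adverse event, and it has no meaning for one who died.

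The way the FAS is built sharpens the problem. A man without a Day 169 value and without an escape enters the FAS only through drug-related discontinuation. The censoring rows for discontinued men therefore do not hold ordinary losses to follow-up, which the FAS has already removed. They hold almost only men whom the plan calls failures.

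The section says its analyses are meant to further validate the primary result. A Kaplan-Meier rate at or above the primary percentage could be read as support when it partly reflects failures that were recoded.

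**Working it through.** **1. The plan's own figures (SAP 2.3).** Inputs: test level and null, "two-sided nominal significance level of 0.05 and null proportion of 85" (per cent); maintenance endpoint, "a sample size of 165 participants has an exact power of 88.3% when the true proportion is 93" (per cent); Day 29 endpoint, "This sample size of 165 participants has a power >99.9% when the true proportion is 97.5" (per cent); drop-out allowance, "Assuming the dropout rate will be around 15%, a sample size of 195 participants in total is planned for this study".

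- Exact binomial test, at most 0.025 in each tail. P(X ≥ 150 | 165, 0.85) = 0.0173 and P(X ≤ 130 | 165, 0.85) = 0.0201, so the test rejects at X ≥ 150 or X ≤ 130.
- Power at 93% = 88.32% (stated 88.3%). Power at 97.5% = 99.9995% (stated >99.9%).
- 165 / 0.85 = 194.1, rounded up to 195.

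All reproduce. I use N = 165 below as a working FAS size.

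**2. Formulas.** Let E be the number of escapes and D the number of castrate men who leave from Week 8 on for a drug-related reason. The documents give neither, so both are assumptions. With no intermittent gaps:

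- Primary under rule (c) = (N − E − D) / N.
- Kaplan-Meier at Week 24 = product over the five visits (Days 57, 85, 113, 141, 169) of (at risk − events) / at risk.

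**3. Example A: E = 8 (2, 2, 1, 1, 2 by visit), D = 5 (2, 1, 1, 1 leaving after the first four visits).**

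- Primary: 152/165 = 92.1%.
- Table 5.1, the five men censored: 163/165 × 159/161 × 157/158 × 155/156 × 152/154 = 95.1%.
- The five men as events: 163/165 × 159/163 × 157/159 × 155/157 × 152/155 = 152/165 = 92.1%.

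The gap is 3.0 points for five men.

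**4. Range.** E = 4, 8 or 12, with escapes and exits placed early, evenly or late:

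| D | Table 5.1 rate minus rate with these men as events (points) |
|---|---|
| 0 | 0 |
| 1 | 0.56 to 0.61 |
| 3 | 1.68 to 1.82 |
| 5 | 2.80 to 3.03 |
| 10 | 5.59 to 6.06 |

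This is about 0.6 points per man; the ceiling is 1/165 = 0.61. In 20,000 random patterns with D ≥ 1 and intermittent gaps allowed, censoring these men gave the higher Kaplan-Meier rate every time.

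**5. Example B, with intervals: E = 12 (2, 3, 3, 2, 2), D = 5 (as above).**

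- Table 5.1: 163/165 × 158/161 × 154/157 × 151/153 × 148/150 = 92.6%, Greenwood 95% CI 88.6 to 96.6%.
- The five men as events: 148/165 = 89.7%. Without censoring, Greenwood reduces to 0.897 ± 1.96 × √(0.897 × 0.103 / 165), or 85.1 to 94.3%.
- Primary: 148/165 = 89.7%, Clopper-Pearson 84.0 to 93.9%.

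**6. A rule that pulls the other way.** Table 5.1 censors a completer at his last value before his first gap, whereas rule (d) counts him as maintained. With E = 12 (as in B), D = 0 and 20 such men (5 after each of the first four visits):

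- Kaplan-Meier: 163/165 × 155/158 × 147/150 × 140/142 × 133/135 = 92.25%.
- Primary: 153/165 = 92.73%.

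In the 20,000 patterns of step 4, the Table 5.1 rate fell below the primary percentage in 159.

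**The case against.** The strongest defence is that a sensitivity analysis is supposed to change an assumption. The event is labelled as an escape event, Sensitivity analysis 4 openly drops the same drug-related exits, and Sensitivity analysis 3 brings in discontinuations for any reason. On this view the set varies the handling of exits around a primary that keeps them as failures. Once recoded, the Kaplan-Meier equals the primary proportion when there are no gaps, so it would add little as a check on exits.

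Part of this stands. An escape-only curve is a legitimate quantity, and the loss of contrast is real. But the SAP does not declare that target. It gives the analysis the co-primary's name, and SAP 5.7.2.1 says that estimands will not be considered.

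Three stronger readings are tempting, and the documents do not support them.

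- *The Kaplan-Meier must exceed the primary percentage.* Step 6 shows that it need not. The upward direction is certain only against the same Kaplan-Meier with these men as events, and only if there is at least one such man.
- *The discontinued-without-escape rows hold only drug-related failures.* A man at or above 50 ng/dL on Day 29 is in the FAS as a failure. If he is castrate from Week 8 and then leaves for another reason, he falls in the same rows, because the table looks for escape only from Week 8.
- *Every drug-related exit conflicts with the primary.* The primary maintenance calculation excludes exits before Week 8, so the conflict with rule (c) starts at Week 8.

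Two further limits stand. After a single injection such exits may be few. The SAP also tabulates withdrawal reasons and adverse events leading to discontinuation, so an attentive reader could see part of what was censored.

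**Conclusion.** The inconsistency is in the text and is worth correcting. Sensitivity analysis 2 carries the co-primary's name but censors castrate men who leave from Week 8 on for a drug-related reason, whom the FAS definition and rule (c) call failures. At an assumed FAS of 165, the Week 24 rate is overstated by about 0.6 points per such man relative to the same analysis with them as events. That is about 3 points for five men and zero for none. The counts are assumptions, so the actual size cannot be known from the documents.

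The effect is confined to one reported sensitivity rate and its interval. The Clopper-Pearson primary is untouched, and because the study is descriptive with no formal test, no type I error is involved. A reader might infer from Example B that the coding alone lifts the lower limit over the 85% planning value. It does not: of the distance from 84.0% to 88.6%, the step from 85.1% to 88.6% comes from the coding, and the step from 84.0% to 85.1% comes from using Greenwood instead of Clopper-Pearson.

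**What to change.** In SAP 5.7.2.3:

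1. Split the discontinued-without-escape rows of Table 5.1 by reason. Add: *left at or after Week 8 for a drug-related reason (adverse event or death), no escape: event on the day of discontinuation*. Keep censoring for other discontinuations.
2. Change the event definition, in the text and in the table footnote, to *escape or drug-related discontinuation*.
3. State that exits before Week 8 are excluded, as in the primary maintenance calculation. Without this limit the new row would create a fresh mismatch.
4. If an escape-only curve is also wanted, label it *escape only* and report beside it how many drug-related exits were censored.

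The cost is one table row and a few sentences. Protocol 7.2 already has the reason for discontinuation recorded in the eCRF, so no new data are needed. The drawbacks are that the rate may be slightly less favourable and, with few intermittent gaps, will lie close to the primary proportion. Item 4 keeps a contrasting analysis for readers who want one.

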7.2 Participant Discontinuation/Withdrawal from the Study

- A participant may withdraw from the study at any time at his/her own request or may be withdrawn at any time at the discretion of the investigator for safety, behavioural or compliance reasons.
- At the time of discontinuing from the study, an early discontinuation visit should be conducted, as shown in the SoA. See SoA for data to be collected at the time of study discontinuation and follow-up and for any further evaluations that need to be completed.
- The reason for discontinuation will be recorded in the eCRF.
- If the participant withdraws consent for disclosure of future information, the sponsor may retain and continue to use any data collected before such withdrawal of consent.
- If the participant withdraws consent for any further contact, the investigator will explain in the medical records that the participant was also withdrawn from study procedures. This information must be entered in the eCRF.
- If a participant withdraws from the study, he/she may request destruction of any samples taken and not tested, and the investigator must document this in the site study records.
- A participant will be withdrawn from the study if they have inadequate testosterone suppression (defined as >50 ng/dL detected at least 30 days after administration of study intervention and on two consecutive measurements at least 2 weeks apart, at either a scheduled or unscheduled study visit).

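### Sensitivity analyses 4 and 5 of the maintenance endpoint leave out men whom the primary analysis counts as failures, so neither is a sound check of that result

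*SAP*

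**What the plan says.** The main analysis is set out in SAP 5.7.2.2: "The two primary endpoints will be tabulated with two-sided 95% CIs separately using the Clopper Pearson exact method for the FAS". For the maintenance endpoint, SAP 5.7.2.1 gives four rules for missing data.

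- Rule (a), escape followed by missing visits: "subsequent missing data is irrelevant; that is to say, participant will be treated as failure in that case".
- Rule (b): a man castrate until he drops out for a reason unrelated to the drug is left out of the calculation.
- Rule (c): a man castrate until he drops out for a drug-related reason, specified as a drug-related adverse event or death, is a failure.
- Rule (d): a man with a gap whose available values are all castrate counts as maintained.

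Men who stop before Week 8 are also left out.

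SAP 5.7.2.3 then adds five sensitivity analyses, introduced as further validation of the primary result. Two matter here.

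- Analysis 4: "Participants in the FAS or PPS who do not discontinue from the treatment period prematurely due to drug-related reasons will be included".
- Analysis 5: "Participants in the FAS or PPS without any missing data from Week 8 to Week 24 will be included".

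Protocol 7.2 states: "A participant will be withdrawn from the study if they have inadequate testosterone suppression". The trigger is two consecutive values above 50 ng/dL, at least 2 weeks apart and at least 30 days after the injection. SAP 4 admits to the FAS only treated men who have baseline, Day 29 and Day 169 testosterone values, or who are treatment failures.

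**The concern.** A sensitivity analysis should vary an assumption behind the primary estimate while leaving the outcome free to go either way. These two choose men partly by their outcome. Under Protocol 7.2, confirmed failure to maintain castration is itself what creates the missing visits, and analysis 5 then uses missing visits as its ground for exclusion. The FAS definition sharpens this: a man with no Day 169 value is in the FAS only if he is a treatment failure, so the early stoppers whom analysis 5 removes from the FAS are failures. Analysis 4 takes out the drug-related drop-outs directly.

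At stake is how the report reads. Estimates above the primary one would appear under a validation label, although part of the gain comes from deleting failures.

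**Working it through.** **Step 1. The plan's own figures.** SAP 2.3 gives n = 165, null proportion 0.85, true proportion 0.93 and two-sided 0.05. The smallest r with P(X ≥ r | 165, 0.85) ≤ 0.025 is r = 150 (tail 0.0173). P(X ≥ 150 | 165, 0.93) = 0.8832, which matches the stated 88.3%. For dropout, 165 / (1 − 0.15) = 194.1, rounded up to 195, also as stated. The present point touches neither figure. They supply a base case: 0.93 × 165 = 153.45, so take 153 maintained and 12 failures.

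**Step 2. Who is kept where.**

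| Man | Primary | Analysis 4 | Analysis 5 |
|---|---|---|---|
| Confirmed escape, withdrawn, a scheduled visit missing | failure (a) | failure | removed |
| Escape, no scheduled visit missing | failure | failure | failure |
| Drug-related drop-out from Week 8 on, no escape | failure (c) | removed | removed |
| Intermittent gap, all available values castrate | maintained (d) | maintained | removed |
| Complete and castrate throughout | maintained | maintained | maintained |

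**Step 3. Analysis 4.** If it removes c failures, the estimate is x/(n − c), which is at least x/n for every c ≥ 0. It can equal or exceed the primary estimate and can never fall below it.

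**Step 4. Analysis 5, failures removed.** The documents do not give the number removed, k. With no rule (d) exclusions the estimate is 153/(165 − k), with Clopper-Pearson limits:

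| k | Estimate | 95% CI |
|---|---|---|
| 0 | 153/165 = 92.7% | 87.6–96.2 |
| 5 | 153/160 = 95.6% | 91.2–98.2 |
| 7 | 153/158 = 96.8% | 92.8–99.0 |
| 10 | 153/155 = 98.7% | 95.4–99.8 |
| 12 | 153/153 = 100% | 97.6–100 |

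The middle rows come from one assumed pattern: all 12 failures are persistent escapes, first seen evenly over Weeks 8, 12, 16, 20 and 24.

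- Confirmed at the next 4-weekly visit: escapes first seen at Weeks 8, 12 and 16 leave a missing visit. 3/5 × 12 = 7.2, about 7.
- Confirmed 2 weeks later: Weeks 8 to 20 do. 4/5 × 12 = 9.6, about 10.
- Confirmed 4-weekly, with the early-withdrawal sample counted as the Week 24 value: Weeks 8 and 12 only. 2/5 × 12 = 4.8, about 5.

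**Step 5. Analysis 5, maintainers removed.** If g rule (d) maintainers also go, the estimate is (153 − g)/(165 − k − g). Assume g = 15. With k = 0 it is 138/150 = 92.0%, and with k = 1 it is 138/149 = 92.6%, both slightly below 92.7%. To offset k = 7 exactly, 5/(158 − g) = 12/165, so 158 − g = 68.75 and g is about 89 of the 153.

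**Step 6. A borderline case.** 149/165 = 90.3% (84.7–94.4) has a lower limit below the 85% used in planning. Removing 4 of the 16 failures gives 149/161 = 92.5% (87.3–96.1), above it.

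**The case against.** The primary analysis keeps rule (a) and (c) failures. Analysis 2 (Kaplan-Meier) counts every observed escape as an event, and analysis 3 does not exclude escapers. The SAP introduces analyses 3 to 5 openly as percentages in different populations, and SAP 5.7.1.1 rules out formal testing. All of this stands: the primary result is untouched and nothing is decided on analysis 4 or 5. It does not make those two informative as validation.

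Table 5.1 of the SAP counts missing values only up to the day of discontinuation. Under that convention withdrawn escapers would stay in analysis 5. But the table holds the censoring rules for analysis 2; analysis 5 does not refer to it and names the whole span to Week 24. At best the text is ambiguous.

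The early-withdrawal sample may fill the last slot, because the visit list in SAP 5.1.1.3 has one combined end-of-study/early-withdrawal entry and SAP 6.2 does no remapping. That lowers the number removed (about 5 instead of 7 in the scenario above) but does not restore escapers with earlier visits missing.

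A reader might go further than the documents allow in three ways.

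- That both analyses can only favour the drug. This is strictly true of analysis 4 alone, since analysis 5 also removes successes under rule (d).
- That withdrawal for escape also empties analysis 4 of failures. It does not: drug-related means adverse event or death, so men withdrawn for escape stay in analysis 4 as failures.
- That analysis 5 loses all failures. It does not: a single unconfirmed escape triggers no withdrawal, and an escape first seen at Week 24, or at Week 20 and confirmed at Week 24, leaves nothing missing.

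**Conclusion.** The point holds on the plain wording. Analysis 5 removes confirmed escapers who were withdrawn early enough to miss a scheduled visit, and also drug-related drop-outs. Its bias is upward unless few failures and relatively many gap-only maintainers are removed. Analysis 4 removes only failures and cannot contradict the primary estimate.

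The size cannot be fixed from the documents. From an assumed 153/165, and ignoring rule (d) exclusions, the analysis 5 estimate lies anywhere from 92.7% (no failure removed) to 100% (all 12 removed). The values 95.6%, 96.8% and 98.7% are scenario figures, which rest on persistent escapes spread evenly over the visits and on how quickly they are confirmed. Unconfirmed escapes would lower the number removed. The SAP should be corrected, but the primary analysis, the sample size and the power do not depend on it.

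**What to change.** In analysis 5, keep every man who is a failure under rule (a) or rule (c) as a failure, whatever is missing afterwards, and apply the completeness requirement only to men who are not failures. Sparing observed escapes alone would not be enough, because rule (c) failures have missing values without an escape and would still be lost. Worded this way, analysis 5 takes out only maintainers with gaps and so tests rule (d): with 12 failures and an assumed 15 such men it would give 138/150 = 92.0% against 92.7%. How the early-withdrawal sample is slotted would then no longer decide whether a failure is counted.

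Drop analysis 4, or label it as excluding rule (c) failures and as not a robustness check of the primary result.

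The cost is SAP wording only, with no new data. The sensitivity results may become less favourable.
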